**Table 8-2 Sampling days and times for PK (for Cycle 3 exclusively, irrespective of nivolumab schedule switch)**

Cycle day Time [h]	Cycle 3										
	1					3	15				17
	0*	0.5 	1.5 	4 	8 	0*	0*	1.5 	4 	8 	0*
Part A											
Nivolumab PK	X	-	X	-	X	X	X	X #	-	-	X
Debio 1143 PK	X	X	X	X	X	X	X	X	X	X	X
Nivolumab ADA	X	-	-	-	-	-	X	-	-	-	-
Part B											
Nivolumab PK	X	-	X	-	-	-	X	X #	-	-	-
Debio 1143 PK	X	-	X	X	-	-	X	X	-	-	-
Nivolumab ADA	X	-	-	-	-	-	X	-	-	-	-

\* To be performed prior to Debio 1143 administration;

 Just before start of nivolumab infusion;

 At the end of nivolumab infusion for patients receiving 240 mg Nivolumab on Day 1 and Day 15 (q4w) or 1.5 hours after Debio 1143 administration for patients receiving 480 mg nivolumab on Day 1 (q4w);

 4 hours after Debio 1143 administration;

 8 hours after Debio 1143 administration;

# PK done for patients remaining under 240 mg nivolumab on Day 1 and Day 15 (q4w),

**Table 8-3 Sampling day and times (for Cycle 6 and EOT exclusively, irrespective of nivolumab switch of schedule)**

Cycle	6		EOT 
Cycle day	1		
Time [h]	0*	1.5 	
Part A and B			
Nivolumab PK	X	-	-
Debio 1143 PK	X	X	-
Nivolumab ADA	X	-	X

\* To be performed prior to Debio 1143 administration;

 At the end of nivolumab infusion;

 At the time of the safety laboratory assessment; For patients entering the Extended study period, the last nivolumab ADA will be collected at C13D1 instead of at EOT.

#### 8.2.4. Pharmacodynamics and predictive biomarkers

**Tumor biopsies** will be collected as follows:

1. An archived biopsy collected at diagnosis and before any prior PD-1/PD-L1 therapy will be provided, if available.
2. An archived biopsy collected after prior PD-1/L1 therapy will be provided; if not available a percutaneous or endoscopic biopsy will be mandatorily collected during screening.
3. A percutaneous or endoscopic biopsy will be performed (to collect fresh tumor tissue) at the end of Cycle 2, if consented and feasible (optional).

PDy and potentially predictive biomarkers in tumor biopsies may include, but are not limited to [REDACTED]

[REDACTED] and markers of cell death and proliferation.

**Blood samples** for PDy measurements will be collected on Days 1 (pre- and 4 h post-dose Debio 1143), 8, 15 and 22 (always predose) of Cycle 1, and on Day 1 of Cycle 3. PDy and potentially predictive biomarkers in blood [REDACTED]

For all PDy and biomarker measurements, the windows of tolerance for sample collection are provided in [Table 8-5](#).

#### 8.2.5. Pharmacogenomics and pharmacogenetics

Blood samples will be collected for mRNA analyses (pharmacogenomics [PGx] PAX gene) at baseline and on Day 15 of Cycle 1 and on Day 1 of Cycle 3. Blood for circulating tumor DNA (PGx ctDNA) will be collected on Day 1 of Cycle 1, 3 and 6. A blood sample will be collected at baseline to explore genetic variations in DMET genes (pharmacogenetics [PGt]) associated with differences in the PK disposition of Debio 1143 in combination with nivolumab.

Back-up samples for PDy, PGx, and PGt will be stored in a sample storage facility pending use for further investigations within the scope of the above- mentioned procedures. The maximum storage period will be 15 years.

DNA and RNA samples for future analyses that are not yet defined will be de-identified and re-coded for improved protection of patient confidentiality and stored for 15 years.

**Table 8-4 Sampling days and times for PDy and biomarkers**

Cycle	1				3	6
Cycle day	1	8	15	22	1	1
Time [h]	0 h	4 h				
████████████████████	X 	X	X 	X 	X 	-
Predictive biomarkers	X 	-	-	-	-	-
PGt	X 	-	-	-	-	-
PGx PAX gene	X 	-	-	X 	X 	-
PGx ctDNA	X 	-	-	-	X 	X 

 Pre-dose

**Table 8-5 Windows of tolerance for PK, PDy and biomarker samples**

Time point	0* (pre-dose)	0.5 	1.5 	4 
Window of tolerance (nivolumab, Debio 1143, ADA, PDy and biomarkers)	[-2h – 0h] before D1143 intake. No tolerance after D1143 intake	Preferred ± 10 min Acceptable ± 15 min	[-5 min – 30 min] before/after end of nivolumab infusion	± 30 min

\* To be performed prior to Debio 1143 administration (i.e. pre-dose samples);

 Just before start of nivolumab infusion;

 At the end of nivolumab infusion;

 4 hours after Debio 1143 administration;

### 8.3. Study procedures

#### 8.3.1. Study plan

A visit assessment schedule is presented in [Table 8-6](#) and a detailed timetable for visits, and PK, PDy are detailed in [Table 8-1](#), [Table 8-2](#) and [Table 8-3](#).

Study procedures must be performed according to the planned time schedule with strict adherence to visit intervals. All patients enrolled in the study will attend the study visits as indicated in the study plan.

Prior to conducting any of the screening tests, the Investigator or designee will fully explain the study to the prospective patient and provide him/her with a copy of the Patient Information Leaflet/ICF.

If the patient is willing to participate in the study, s/he and the Investigator or designee will both sign the document. Of note, CT or MRI scans done before screening, as part of the patient's standard of care, if within the accepted window up to 8 weeks ( $\pm 1$  week) before C1D1, can be used instead of repeating a new assessment at screening even if it was done before ICF signature, with patient specific agreement, if deemed clinically appropriate by the Investigator. A separate ICF will be signed for participation in the PGx part of the study (section [8.2.4](#)).

Patients will attend the screening visit(s) within 4 weeks prior to the first treatment cycle. The patient's suitability for the study will be confirmed by the inclusion/exclusion criteria (see section [6](#)).

**Table 8-6 Schedule of assessments**

CYCLE DAY*	Screening	CYCLE														EOT	Follow-up#	EOS			
		Baseline		1					2		3				4-13				>13 		
		1	3 	8	15	17 	22	1	15	1	3 	15	17 	1	15				1	15	
INFORMED CONSENT	X	-	-	-	-	-	-	-	-	-	-	-	-	-	-	-	-	-	-	-	
MEDICAL AND MEDICATION HISTORY 	X	X	-	-	-	-	-	-	-	-	-	-	-	-	-	-	-	-	-	-	
INCLUSION/EXCLUSION CRITERIA	X	X	-	-	-	-	-	-	-	-	-	-	-	-	-	-	-	-	-	-	
PHYSICAL EXAMINATION	X 	X	-	-	X	-	-	X	X	X	-	X	-	X	-	X	-	X	-	-	
ECOG, VITAL SIGNS	X	X	-	X	X	-	X	X	X	X	-	X	-	X	X	X	-	X	-	-	
CONCOMITANT MEDICATIONS	X	X	X	X	X	X	X	X	X	X	-	X	-	X	X	X	-	X	X	-	
DIGITAL, TRIPPLICATED 12-LEAD ECG 	X	X	-	X	X	-	X	-	-	X	-	-	-	-	-	-	-	-	-	-	
SAFETY LABORATORY SAMPLING 	X 2a,b,c,f	X 2c,e	X 2d	X 2c	X 2c,e	X 2d	X 2c	X 2c,e,f	X 2c	X 2c,e,f	-	X 2c	-	X 2c,e,f	-	X 2c,e,f	-	X 2c,e	-	-	
PREGNANCY TEST 	X	X	-	-	-	-	-	X	-	X	-	-	-	X	-	X	-	X	X	-	
CT SCAN OR MRI 	X	-	-	-	-	-	-	-	X	-	-	-	-	-	X	X	-	X	X	-	
TUMOR BIOPSY 	X	-	-	-	-	-	-	-	-	Optional	-	-	-	-	-	-	-	-	-	-	
PK SAMPLING 	-	X	X 6a	X	X	X 6a	X	-	-	X	X 6a	X	X 6a	X 6b	-	X 6b	-	X 6b	-	-	
PDY AND PREDICTIVE BM SAMPLING 	-	X	-	X	X	-	X	-	-	X	-	-	-	X 7a	-	-	-	-	-	-	
DEBIO 1143 DISPENSING/ACCOUNTABILITY 	-	X	-	-	X	-	-	X	X	X	X	X	-	X	X	X	-	-	-	-	
NIVOLUMAB DISPENSING/ACCOUNTABILITY 	-	X	-	-	X	-	-	X	X	X 9a	-	+/-	-	X 9a	+/-	X 9a	+/-	-	-	-	
ADVERSE EVENTS	X	X	X	X	X	X	X	X	X	X	X	X	X	X	X	X	-	X	X 	-	

**Cycle:** Each cycle is defined as of 28 days

**EOT:** A visit should be performed 30 days (± 5days) after last Debio 1143 dose, unless start of new cancer treatment or end-of-life care before, in which case EOT visit should be ideally scheduled immediately before these events.

**Follow-up:** A first follow-up (FU) visit is scheduled 90 (± 15) days after last study treatment, a second safety follow-up visit may be scheduled at 5 months (±15 days) after the last nivolumab infusion, provided the first safety follow-up visit did not overlap (± 1 week), and provided that no subsequent anticancer treatment or end-of-life hospice care had been started before. Subsequent visits will be scheduled every 12 weeks (± 1 week) after EOT unless confirmed or symptomatic PD occurred before or any new anticancer treatment or end-of-life care is started, whichever occurs first. Once PD occurs, or start of new treatment, phone calls, email or mail to document survival status will be done every 4 (± 1) months until the end of the Main study period (lasts until 18 months after LPI or 60 days after LPLV, whichever occurs first).

**EOS:** At the end of the Main study period or at LPLV if patients are ongoing in the Extended study period, whichever occurs last.

- \* Examinations should be performed in the following order as applicable: physical examination, vital signs, ECG, safety blood/urine samples, followed by blood sampling for PK/PDy according to specific instructions, and other examinations: Note: ECGs always have to be taken before PK/PDy sampling. Assessments should be performed on schedule, but occasional changes may be allowed. If the study schedule is shifted, both assessments and dosing must be shifted to ensure the collection of data is completed prior to dosing. **Windows:** Laboratory assessments and clinical examinations: Screening period: -4 days (i.e., day -32); EOT visit: ±5 days; follow up visits ±1 week, in case of holidays, vacations; other administrative reasons: ± 3 days in all cycles. Window for CT/MRI assessment = ± 1 week
- # Assessments for concomitant medications, pregnancy test and AEs will be performed only at the first two FU visits, if applicable. CT scan or MRI assessments will be performed until confirmed iRECIST PD, symptomatic PD or any new anticancer treatment or end-of-life hospice care is started or until EOS whichever occurs first.
- # Height only collected at screening.
- 1 Digital triplicate 12-lead ECGs will be recorded after 10 minutes of supine rest at the following 3 time points: pre-, 0.5-2h Debio 1143 post-dose (before starting the nivolumab infusion or after nivolumab perfusion was removed) and 4-6 h post-dose; There should be at least 1 minute between each ECG and all 3 ECGs should be completed within 10 minutes or less. ECG readings must be performed before PK/PDy sampling. ECG reading will be done centrally and also locally for screening purposes.
- 2 Pre-dose (as per section 8.2.2.5) only required if screening test were performed > 7 days prior to C1D1 or if inclusion/exclusion criteria were not met during screening:
- 2a HIV, HCV and HBV serology testing and CPK and Troponins (I or T whichever is applicable): Only at screening, to be repeated if clinically indicated only.
- 2b FSH/LH and total testosterone (in male) or estrogens (in female patients), free-cortisol (at morning) and ACTH: Only at screening and to be repeated if clinically indicated.
- 2c Hemoglobin, hematocrit, platelets and complete blood cell count and differential counts, creatinine, sodium, potassium, calcium, total bilirubin (if >ULN, then also measure direct bilirubin), ALP, AST, ALT, amylase, lipase, LDH, total protein, albumin, CRP.
- 2d Part A patients (only): Total bilirubin (if >ULN, then direct bilirubin should also be measured), ALP, AST, ALT, and creatinine.
- 2e TSH, FT3 and FT4: At Day 1 and Day 15 in Cycle 1 and every Day 1 of each subsequent cycle.
- 2f CA-125 to be performed at screening within 4 weeks of C1D1, exclusively in applicable patients included in Cohort 4, and to be repeated before start of each new cycle if abnormally elevated before treatment start, unless PD, any new anticancer treatment or end-of-life hospice care is started before.
- 3 In women of childbearing potential only: blood test at screening (only required if screening test were performed > 7 days prior to C1D1), then urine dipstick test alone would be sufficient, at the beginning of each treatment cycle while on study up to 5 months after EOT.
- 4 Every 8 weeks (±1 week) from first on-treatment scan until Cycle 10, then from Cycle 13, every 12 weeks (± 1 week) until confirmed iRECIST PD, symptomatic PD or any new anticancer treatment or end-of-life hospice care is started or until the end of the Main study period whichever occurs first. For patients who continue study treatment in the Extended study period, tumor response assessments will be performed at the frequency of local institutional care practice until EOT. All patients will have CT or MRI at the time of disease progression, if none previously available. CT or MRI done before screening, as part of patient's standard of care and not older than 8 weeks (+1-week tolerance) before C1D1 can be used instead of repeating a new assessment at screening even if done before ICF signature with patient specific agreement, if deemed clinically appropriate by the Investigator. A contrast enhanced brain CT or MRI is mandatorily at baseline only in SCLC cohort, subsequent brain scans to be done if clinically indicated.
- 5 Up to 3 tumor tissue samples will be collected:
- 1) An archived biopsy at diagnosis (before prior PD-1/PD-L1 therapy) = optional;
- 2) An archived biopsy if collected after prior PD1/PD-L1 or, if not available a fresh biopsy collected at screening will be mandatory;
- 3) A fresh biopsy collected at end of Cycle 2 (day 28=Day 1 of the following cycle) = optional
- 6 Timepoints as specified in Table 8-1, Table 8-2 and Table 8-3 and windows of tolerance as specified in Table 8-5.
- 6a Patients included in Part A only.
- 6b Debio 1143 PK, nivolumab PK, and nivolumab ADA sample at C6D1 only. In addition, for patients discontinuing the study at the end of the Main study period, the last nivolumab ADA will be collected at EOT, and for patients entering the Extended study period, the last nivolumab ADA will be collected at C13D1 instead of at EOT.
- 7 Timepoints as specified in Table 8-4 and windows of tolerance as specified in Table 8-5.
- 7a Only at Cycle 6: PGx ctDNA.
- 8 Debio 1143 will be taken orally on D1-10 and D15-24 on an empty stomach (patients will fast for 2 h before dosing and for at least 1 h after dosing) at approximately the same time each day. Water is permitted freely. A missed dose can be taken as soon as the patient remembers but no later than 6 h after the planned dose. If >6 h have elapsed, the missed dose should be skipped and the next dose taken according to the regular dosing schedule. A double dose should not be taken to make up for a missed dose. Debio1143 will be given in the hospital (before nivolumab infusion whenever is applicable) during: Cycle 1 on Days 1,3 (only Part A), 8, 15, 17 (only Part A), 22; Cycle 2 on Days 1 and 15; Cycle 3 on Days 1, 3 (only Part A), 15, and 17 (only Part A); and on Days 1 ± 15 of all subsequent cycles. The rest of the days will be taken at home following relevant medical instructions. A patient's diary to record treatment compliance will be provided as a separate document and it will be reconciled with the returning capsules by the study nurse.
- 9 Nivolumab will be administered, as per current prescribing information, at a dose of 240 mg, flat dose by IV infusion over at least 30 minutes on Days 1 and 15, every 4 weeks (i.e., 2 infusions in each cycle).
- 9a From Cycle 3 on, the switch to an administration of 480 mg of nivolumab only on Day 1 of each 28-day cycle is allowed based on the Investigator's judgment and Sponsor's agreement.
- ± Dispensing of nivolumab will depend on the nivolumab schedule administered from Cycle 3 onwards.

-  Continuous AE monitoring, with Investigator's assessment and documentation at scheduled study visits up to EOT visit and second follow up visit, if applicable. The SAE reporting period is up to 5 months after the last nivolumab administration. Patients continuing in follow-up (FU) after EOT, in the first and/or second FU visits will have final AEs update of any ongoing toxicity at this time, if applicable, unless start of new anticancer treatment or end-of-life-care, in which case visit should be scheduled ideally before.
-  For Part B, visits on Cycle 1 and Cycle 3 on Days 3 and 17 will not be performed
-  Including information on current and previous tobacco and alcohol use/consumption
-  Only applicable for patients treated beyond Cycle 13

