-  Every 8 weeks (±1 week) from first on-treatment scan until Cycle 10, then from Cycle 13, every 12 weeks (± 1 week) until confirmed iRECIST PD, symptomatic PD or any new anticancer treatment or end-of-life hospice care is started or until the end of the Main study period, whichever occurs first. For patients who continue study treatment in the Extended study period, tumor response assessments will be performed at the frequency of local institutional care practice until EOT. All patients will have CT or MRI at the time of disease progression, if none previously available. CT or MRI done before screening, as part of patient's standard of care and not older than 8 weeks (+1 week tolerance) before C1D1 can be used instead of repeating a new assessment at screening even if done before ICF signature with patient specific agreement, if deemed clinically appropriate by the Investigator.  
A contrast enhanced brain CT or MRI is mandatorily at baseline only in SCLC cohort, subsequent brain scans to be done if clinically indicated.
-  Up to 3 tumor tissue samples will be collected:
- 1) An archived biopsy at diagnosis (before prior PD-1/PD-L1 therapy) = optional;
  - 2) An archived biopsy if collected after prior PD1/PD-L1 or, if not available a fresh biopsy collected at screening will be mandatory;
  - 3) A fresh biopsy collected at end of Cycle 2 (day 28=Day 1 of the following cycle) = optional
-  Timepoints as specified in [Table 8-1](#), [Table 8-2](#) and [Table 8-3](#) and windows of tolerance as specified in [Table 8-5](#).
- 6a Patients included in Part A only.
  - 6b Debio 1143 PK, nivolumab PK, and nivolumab ADA sample at C6D1 only. In addition, for patients discontinuing the study at the end of the Main study period, the last nivolumab ADA will be collected at EOT, and for patients entering the Extended study period, the last nivolumab ADA will be collected at C13D1 instead of at EOT.
-  Timepoints as specified in [Table 8-4](#) and windows of tolerance as specified in [Table 8-5](#).
- 7a Only at Cycle 6: PGx ctDNA.

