### 6.1. Inclusion criteria

The same tumor types are eligible in Part A and B.

All patients must fulfil all the following criteria (both Parts A and B, unless specified otherwise):

1. Willing and able to sign a written informed consent form;
2. Male or female  $\geq 18$  years of age.
3. Histologically and/or cytologically confirmed advanced/ unresectable or metastatic solid tumor for one the following indications:
  - a. SCLC
  - b. SCCHN (except nasopharyngeal carcinoma)
  - c. GI cancers, including esophageal, gastric, colorectal or pancreatobiliary with known MSI-H/MMRd or any other known DDRs abnormalities, including HRD
  - d. Platinum-resistant\* EOC, endometrial cancer, PPC or cervical cancer, with known MSI-H/ MMRd, hereditary/somatic mutations of the BRCA1 and BRCA2 genes or other known DNA DDRs abnormalities (incl. HRD)  
\* Platinum-resistant is defined as relapse or progressive disease (PD) occurring within 1 to 6 months (180 days) after a platinum-containing chemotherapy.
4. Have received at least one prior line of standard systemic chemotherapy in the advanced/unresectable cancer setting (standard adjuvant/neoadjuvant treatment is acceptable if

- relapse occurred within six months of treatment end) and have no established standard therapeutic alternatives.
5. Have progressed or relapsed during or after a prior anti-programmed cell death-1 (PD-1)/programmed cell death-ligand 1 (PD-L1)-based treatment, given either as a single agent or in combination with standard/approved chemotherapy, tyrosine kinase inhibitors (TKIs), radiotherapy (RT) or other monoclonal antibodies (mAbs) that are not known to modulate/inhibit immune checkpoints (CPIs)
  6. Minimum washout periods since prior therapy until treatment start (C1D1) (in cases of more than one prior treatment type, whichever has the longest minimum period applies):
    - a. 3 weeks for chemotherapy (6 weeks, specifically for nitrosoureas or mitomycin C containing regimens);
    - b. 4 weeks for any prior mAbs or live vaccines; for any investigational mAbs 4 weeks or at least the duration of one treatment cycle whichever is longest
    - c. 3 weeks for prior RT (1 week in case of localized antalgic/hemostatic hypofractionated RT flash)
    - d. 2 weeks for TKIs, hormonal therapy, other anti-cancer treatment not previously specified or investigational agents
    - e. 4 weeks for any major surgery

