### 8.2.1.3. Tumor response criteria

For the evaluation of target lesions by the RECIST v1.1 criteria, following definitions will be applied (38):

- **CR:** Disappearance of all target lesions. Any pathological lymph nodes must have reduction in short axis to  $< 10$  mm. CR must be confirmed by repeat assessments performed no less than 28 days after the criteria for response are first met to qualify as CR.
- **PR:** At least a 30% decrease in the sum of diameters of target lesions taking as reference the baseline sum diameter. PR must be confirmed by repeat assessments performed no less than 28 days after the criteria for response are first met to qualify as PR.

- **Progressive Disease (PD):** At least a 20% increase in the sum of diameters of target lesions, taking as reference the smallest sum on study (this includes the baseline sum if that is the smallest on study). In addition to the relative increase of 20%, the sum must also demonstrate an absolute increase of at least 5 mm. Note: the appearance of one or more new lesions is also considered progression.
- **Stable Disease (SD):** Neither sufficient shrinkage to qualify for PR, nor sufficient increase to qualify for disease progression, taking as reference the smallest sum diameter while on study.

As per the GCIG criteria (Cohort 4, if applicable), a CA-125 response is defined as at least a 50% reduction in CA-125 levels from a pretreatment sample for patients whose CA-125 level was greater than twice the upper limit of the reference range when they started treatment.

Progressive disease definitions are provided in [Appendix C: Response to treatment criteria](#).

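### The RECIST baseline may be a routine-care scan up to 9 weeks old, and nothing requires it to follow the last prior anticancer therapy

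*Protocol*

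**What the plan says.** Three places in the Protocol let an existing scan replace the screening scan. Footnote 4 of Table 8-6 accepts one "not older than 8 weeks (+1-week tolerance) before C1D1 can be used instead of repeating a new assessment at screening". Footnote 4 of Table 1-1 has the same rule: "not older than 8 weeks (+1 week tolerance) before C1D1 can be used instead of repeating a new assessment at screening". Section 8.3.1 accepts scans done "as part of the patient's standard of care, if within the accepted window up to 8 weeks", with the tolerance written as plus or minus one week; the maximum is the same. The conditions are the patient's agreement and the qualifier "if deemed clinically appropriate by the Investigator".

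The washouts are in Section 6.1, criterion 6. For chemotherapy: "3 weeks for chemotherapy (6 weeks, specifically for nitrosoureas or mitomycin C containing regimens". For radiotherapy: "3 weeks for prior RT (1 week in case of localized antalgic/hemostatic hypofractionated RT flash". TKIs, hormonal and other agents need 2 weeks; antibodies and major surgery need 4 weeks (for investigational antibodies, one treatment cycle if that is longer). Exclusion 1 in Section 6.2 separately bars thoracic or head-and-neck radiation above 30 Gy in the 6 weeks before C1D1.

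Section 8.2.1.3 defines partial response as "At least a 30% decrease in the sum of diameters of target lesions taking as reference the baseline sum diameter". SAP Section 7.2 takes the last non-missing value before first dose as baseline and sets no maximum age. SAP Section 6.5 asks only that a baseline tumor assessment exists.

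**The concern.** A response rate without a control arm relies on the baseline to separate the effect of study treatment from what came before. Here the baseline can predate the end of the previous therapy. A patient scanned at Day -60, then given a TKI until Day -14, breaks no washout or scan-timing rule, and any shrinkage from the TKI is measured as response to Debio 1143 plus nivolumab. With no therapy in between, up to 9 weeks of untreated growth lies between the reference scan and first dose and must be reversed before a response can register.

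Criterion 7 does not prevent this. It asks for progression on or after PD-1/PD-L1 therapy, not on the baseline scan and not after the most recent line. The same endpoint is handled more tightly elsewhere: a CA-125 baseline must fall within 2 weeks of treatment start (Protocol 8.2.1.1), and archived tissue must postdate PD-1/PD-L1 failure (criterion 10).

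At stake are confirmed ORR, the Part B primary endpoint, and unconfirmed ORR, which drives two binding futility stops per cohort of at most 15 patients.

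**Working it through.** **1. The plan's own boundaries.** With prior Beta(0.5, 0.5), the posterior is Beta(0.5 + r, 0.5 + n - r).

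- Futility, stop if P(rate ≤ 0.05) > 0.20: 0/8 gives 0.643 (stop), 1/8 gives 0.149 (continue), 1/11 gives 0.223 (stop), 2/11 gives 0.041 (continue).
- Efficacy, claim if P(rate > 0.15) ≥ 0.80: 3/15 gives 0.726 (no claim), 4/15 gives 0.892 (claim).

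These reproduce the stated rules: 0 of 8, at most 1 of 11, at least 4 of 15. At each boundary one patient separates the two decisions.

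**2. Time for therapy after the baseline scan.** Maximum scan age is 8 × 7 + 7 = 63 days. The gap is scan age minus minimum washout. The last column uses a 28-day limit for comparison.

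| Prior therapy | Washout (days) | Gap at 63 days | Gap at 28 days |
|---|---|---|---|
| RT flash | 7 | 56 | 21 |
| TKI, hormonal, other | 14 | 49 | 14 |
| Chemotherapy; RT generally | 21 | 42 | 7 |
| Antibody | 28 | 35 | 0 |
| Nitrosourea, mitomycin C | 42 | 21 | none |
| Thoracic or head-and-neck RT > 30 Gy (exclusion 1) | 42 | 21 | none |

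For investigational antibodies with a cycle longer than 4 weeks the gap is shorter, and it closes only if the cycle lasts 9 weeks or more. Shortening the window narrows the carry-over gap but does not close it; ordering the scan after the last therapy does.

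**3. Effect on the response threshold.** If the sum of diameters changes by a fraction s between scan and first dose, the on-study change needed for PR is 0.70/(1 + s) - 1. The documents give no value for s.

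| s before first dose | On-study change needed for PR |
|---|---|
| -30% | 0% |
| -20% | -12.5% |
| 0 | -30% |
| +20% | -41.7% |
| +30% | -46.2% |

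**4. Size of untreated growth (assumption).** With exponential growth, the diameter ratio is 2^(t/(3 × VDT)), where VDT is the volume doubling time.

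| VDT (days) | 63 days | 28 days |
|---|---|---|
| 30 | +62% | +24% |
| 60 | +27% | +11% |
| 120 | +13% | +6% |

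At VDT 60 and 63 days, a true 30% shrinkage from the first-dose state reads as 1.275 × 0.70 - 1 = -11%, which is stable disease. PR then needs 1 - 0.70/1.275 = 45% true shrinkage.

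**5. Illustration only.** The chance of passing both futility looks is 1 - (1-p)^8 - 8p(1-p)^10. It is 0.564 at p = 17% and 0.413 at p = 13%. The 13% is chosen to show sensitivity; it does not come from step 4.

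**The case against.** The sponsor can say that a new scan is the default, that reuse needs investigator judgement, and that a routine scan showing progression on the last line will often follow that line. Treating after the scan also fits poorly with a population that has no standard alternatives left and capped prior lines. All of this bears on frequency, and frequency is unknown. It does not supply the missing rule on order, and the growth problem needs no intervening therapy.

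Exclusion 1 does limit one case: high-dose thoracic or head-and-neck RT leaves 21 days, not 42.

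Some stronger readings are tempting but not supported:

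- *Old baselines end treatment wrongly.* Treatment ends on symptomatic or iRECIST-confirmed progression (Protocol 5.3, 8.3.2.1), and asymptomatic unconfirmed progression may be treated through with Sponsor agreement (8.2.1). RECIST progression also needs a 5 mm absolute increase.
- *The bias can never be examined.* SAP Section 13 lists start and end dates of prior systemic therapy and RT, and Section 17.3.2 lists lesion assessments.
- *Day -32 is the imaging window.* The 4-day tolerance in the table notes covers laboratory and clinical examinations; CT/MRI has its own tolerance of plus or minus one week.
- *The design loses power from 56% to 41%.* No figure in the documents links scan age to that fall.

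**Conclusion.** The concern holds as a gap in the rules. A compliant baseline scan can be 63 days old and can precede 21 to 56 days of further anticancer therapy, depending on type. Neither SAP Section 7.2 nor the repeat on the ITT/Safety set (17.1.4) addresses it, and Section 8.4 rules out subgroup analyses.

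The interval arithmetic rests only on the documents. The effect on tumor size does not: growth of 13% to 62% over 63 days assumes doubling times of 120 down to 30 days, and carry-over shrinkage cannot be quantified. Bias may go either way. It alters a decision only where a cohort sits at 0 versus 1 of 8, 1 versus 2 of 11, or 3 versus 4 of 15.

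SAP Section 4.3 already refers to futility of the Part B cohorts. A reader might infer that stale baselines caused it. The documents do not support that, because they do not say how many patients entered on a reused scan or how old those scans were.

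**What to change.** 1. In footnote 4 of Tables 1-1 and 8-6 and in Section 8.3.1, require the baseline scan to be done after the last dose of any prior anticancer therapy, including RT. This closes the carry-over gap.
2. In place of 8 weeks plus 1 week, limit a reused routine-care scan to the 4-week screening period. State the imaging tolerance explicitly and consistently with the CT/MRI window in the table notes. This limits untreated growth. Scans made before consent stay usable if they meet both conditions.
3. For patients already enrolled, list the scan-to-C1D1 interval and any anticancer therapy given in between. Repeat confirmed and unconfirmed ORR without patients whose baseline scan was older than the screening window or preceded the end of prior therapy. With the SAP already reporting futility, this is the part that can still inform Part B. It is descriptive and does not reopen a binding stop.

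Cost: amendment wording, plus one listing and one sensitivity table from data already planned for listing. Some patients would need the screening scan that is already scheduled instead of reusing an old one, with a possible short delay to first dose.
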